**Figure 1: Sickled Red Blood Cells and Neutrophils Occlude Vasculature**

The underlying pathogenesis of RBC sickling is the deoxygenation of HbS, which results in polymerization of the hemoglobin, distortion of the RBC, and loss of deformability of the cell. These “sickled” RBCs are a primary component of the occlusive process and cause vascular injury through interactions with endothelial cells.

The other primary component is adhesion, since the stickiness of the cells causes cell aggregates of WBC-RBC, WBC-WBC, and WBC-platelet to form. This adhesion is selectin-mediated and contributes to the VOC process. Cell aggregates block the vasculature and create a trap for the sickled RBCs, resulting in obstruction of blood flow.

Finally, vaso-occlusion resulting from sickled and adherent RBCs also causes slowing of blood flow in post-capillary venules, local tissue hypoxia, and further tissue inflammation, resulting in more deoxygenation and sickling of RBCs, and propagation of the occlusion. This is sometimes called secondary recruitment of sickled cells and occluded vessels. Diapedesis (leukocyte migration into the tissues) and sickle-related microvascular occlusion also take place in postcapillary venules. Pain is the result of initial and ongoing occlusion and ischemia and is thought to be nociceptive. It is particularly severe for patients with the SCD-SS genotype, who have been observed to have a higher mortality than other genotypes.

Of note is that soluble E-selectin, vascular cell adhesion molecules-1 (VCAM-1), and intracellular adhesion molecules-1 (ICAM-1) levels are higher in sickle cell patients at baseline than in normal volunteers. Further evidence suggests that soluble E-selectin and ICAM-1 are increased during acute VOC when compared to baseline in patients with SCD. In addition, increased soluble E-selectin levels have been shown to correlate with increased mortality in SCD patients. Leukocytes adherent to the endothelial cell wall in postcapillary and collecting venules interact with sickled RBCs, leading to vaso-occlusion in sickle-cell mice. However, sickle cell mice lacking E- and P-selectin were protected from developing vaso-occlusion. An understanding of the role that selectins play in cell aggregation and the pathophysiology of VOC is increasing.

### **1.3 Treatment of Vaso-Occlusive Crisis**

Nonpharmacologic management of pain includes cutaneous stimulation (transcutaneous electrical nerve stimulation), heat, cold, vibration, distraction, relaxation, massage, music, guided imagery, self-hypnosis, self-motivation, acupuncture, and biofeedback.

i Nociceptive pain is initiated by nociceptors, the nerves that sense and respond to damage (fractures, burns, bumps, bruises, and inflammation) in a particular part of the body. This differs from neuropathic pain, which is the result of an injury or malfunction in the peripheral or central nervous system (CNS) and which sometimes also occurs in sickle cell disease.

Pharmacologic management of pain includes the use of 3 major classes of compounds: non-opioids (nonsteroidal anti-inflammatory drugs [NSAIDs], topical agents, tramadol, and corticosteroids), opioids, and adjuvants (antihistamines, antidepressants, benzodiazepines, and anticonvulsants). Adjuvant treatments for pain are typically used for chronic pain. NSAIDs are the first line of therapy for acute VOC pain, and are typically prescribed on an outpatient basis. Opioids in repeated and increasing doses are usually the first line of treatment for emergency department or inpatient care required for acute VOC. Common drugs include codeine (oral, for mild pain); or for moderate to severe pain, IV morphine, or morphine-equivalent opioids such as oxymorphone, levorphanol, fentanyl, and methadone. Opioid agonists may also be used in the management of sickle cell pain in adults. They decrease or modify the perception of pain at the level of the CNS.

Studies of pain in the emergency room setting have shown that changes in pain that are clinically significant to the patient are 1.3-1.5 cm on a 10 cm visual analog scale (VAS). Further, smaller studies of pain in the setting of sickle cell vaso-occlusive crisis lend support to this size of change being pertinent for sickle cell pain as well.

Other supportive measures for VOC include hydration, supplemental oxygen, transfusion, and treatment of any concurrent infections or other inciting medical conditions. No treatment is available to interfere with the sickling or vaso-occlusive process.

Current long-term medical management of SCD includes use of hydroxyurea, which is used to increase Hb F (fetal hemoglobin) concentration and reduce the number of pain crises by preventing their development.

#### **1.4 Intravital Microscopy**

Intravital microscopy (IVM) is a non-invasive imaging technique used for studying dynamic cell interactions and microvascular morphometry in living tissue. Variations of this technique have been used to measure microvascular blood flow and perfusion in both human and animal studies for multiple diseases, including diabetes, cardiovascular disease, and more recently SCD. Some sites with the capability to perform IVM on sickle cell patients may include this in the study, as described in this study protocol.

#### **1.5 Biomarkers**

Individuals with SCD display markers and the phenotype of a chronic mild inflammatory condition. Some markers which have been explored in the past include adhesion molecules (selectins, integrins, and activated integrins), cell-cell aggregates, C-reactive protein (CRP), and other markers of cell adhesion and tissue inflammation. Biomarker experiments in this study will be designed to determine whether GMI-1070 affects any such markers in the setting of VOC. Some biomarkers previously studied in SCD are noted below.

Kato, et al measured levels of soluble endothelium-derived adhesion molecules in patients with SCD not in crisis (steady state). Soluble E-selectin (sE-selectin), sP-selectin, sVCAM-1, and ICAM-1 were measured and all were statistically significantly elevated except ICAM-1. All 4 adhesion molecules were elevated and showed a statistically significant relationship to each other with the exception of sICAM-1 to sP-selectin. The presence of sE-selectin in the blood was positively associated with hepatic dysfunction, reticulocyte count, triglyceride level, and linked independently to levels of CRP. Over a 4-year period, mortality was strongly and significantly ( $P=0.002$ ) associated with levels of sE-selectin in the blood whereas no significant correlation was seen with levels of sP-selectin ( $P=0.36$ ). These results suggest that early mortality in SCD patients is associated with endothelial activation.

Wun, et al reported that monocytes are activated in SCD patients, which may be related to the increased occurrence of platelet adherence and aggregation. The mean percentage of platelet-monocyte aggregates (PMA) in Caucasian controls is 14%, whereas African-Americans is 25%, and in SCD patients is 45%.

Okpala, et al published data showing high expression of  $\alpha M\beta 2$  integrins (MAC-1), CD18, and CD62L (L-selectin) on neutrophils of SCD patients. Lum, et al showed that steady state SCD patients expressed elevated levels of MAC-1 and *activated* CD18 on neutrophil surfaces.

Zennadi, et al demonstrated that RBC adhesion to peripheral blood mononuclear cells induced an E-selectin mediated adhesion to endothelial cells. Hidalgo, et al published a paper showing that E-selectin is crucial in activating  $\beta 2$  integrins (MAC-1) at the leading edge of crawling neutrophils to bind and capture RBCs and platelets.

Belcher, et al have reported a 12-fold increase in CRP levels in sickle cell serum compared to normal serum. As stated above, Kato, et al showed a correlation (albeit independent) between sE-selectin and CRP levels in the blood of sickle cell patients.

## 1.6 Nonclinical Information

Nonclinical testing of GMI-1070 has been performed in mice, rats, rabbits, and cynomolgus monkeys. Pharmacodynamic studies have demonstrated that GMI-1070 administration can inhibit selectin binding and biological activity as it relates to induction of selectin-mediated inflammation. Single-dose IV pharmacokinetic (PK) studies in mice (20 mg/kg), rats (20 mg/kg), and monkeys (150 mg/kg), showed a similar half-life ( $t_{1/2}$ ) for mice, rats, and monkeys (1.25 hours, 1.4 hours, and <3 hours, respectively).

The 14-day repeat-dose IV toxicology studies showed a no observed adverse effect level in mice of 150 mg/kg, and in cynomolgus monkeys of 75 mg/kg. Monkeys used in this pivotal toxicology study ranged in age from 21 to 35 months (mean 29 months) – the human age equivalent of 11-12 years.

A 7-day repeat-dose IV toxicology study in juvenile rats showed a no observed adverse effect level of 150 mg/kg/day, and a 14-day repeat-dose IV toxicology study in juvenile rats of 35 mg/kg/day.

In the presence of human, rat, mouse, and monkey hepatocytes, GMI-1070 was metabolically stable.

Additional information may be found in the Investigator's Brochure.

## **1.7 Clinical Information**

A summary of clinical information from 2 clinical studies (GMI-1070-101 and GMI-1070-102), and preliminary data from a third study (GMI-1070-103), is provided in the following sections. Additional information may be found in the Investigator's Brochure.

### **1.7.1 Safety**

Study GMI-1070-101 evaluated single doses of IV GMI-1070 at 2, 5, 10, 20, and 40 mg/kg. Study GMI-1070-102 evaluated multiple doses of 5, 10, and 20 mg/kg given every 8 hours for 4 days, and a loading dose of 40 mg/kg followed by multiple doses of 20 mg/kg given every 8 hours for 2 days. These studies evaluated a total of 72 healthy adult subjects (54 active, 18 placebo).

A third study, GMI-1070-103, recently completed enrollment. This was an open-label study of IV GMI-1070 in adults with stable SCD. Fifteen subjects have received a 20 mg/kg dose followed by a 10 mg/kg dose of IV GMI-1070.

GMI-1070 has demonstrated excellent safety and tolerability in these studies as demonstrated by:

- No clinically significant electrocardiogram or physical exam findings
- With 1 exception, all adverse events (AEs) in subjects receiving GMI-1070 were Grades 1 or 2. Severe symptomatic anemia (grade 4) that occurred in 1 subject with stable SCD, was considered to be remotely related to the study medication, and was resolved with therapy.
- No serious AEs (SAEs) occurred

In both healthy adult studies, mild local irritation at the site of IV administration was observed to occur more frequently in higher dose groups with multiple doses, in both the GMI-1070 and placebo treatment groups. Two subjects in the 40 mg/kg dose group of the phase 1 studies developed a rash. One of these was in Study GMI-1070-101 and received a single dose of GMI 1070 (40 mg/kg), and 1 subject was in Study GMI-1070-102 and received 3 doses of GMI-1070 (a single 40 mg/kg dose, and two 20 mg/kg doses). None of these observations prevented dose escalation or progression to the next study.

Local irritation (Grade 1) was reported in one subject in Study GMI-1070-103.

Headache was reported in 21 subjects (19 active, 2 placebo) across all three studies to date. One subject in Study GMI-1070-102 who received placebo reported a severe (Grade 3) headache; all others (including all reported in subjects receiving GMI-1070) were Grade 1 or 2. Table 2 summarizes all treatment-emergent adverse events (TEAE) across all three IV GMI-1070 studies.

The elevated peripheral WBC and neutrophil counts may reflect the prevention or interruption of adhesion of neutrophils to the endothelial cells on the blood vessel wall, which would be predicted by the selectin-inhibition mechanism of the drug.

It was concluded by the investigators and the Medical Monitor that for studies GMI-1070-101, GMI-1070-102, and GMI-1070-103, all doses observed demonstrated minimal safety concerns for continuing clinical trials at the already tested dose levels, up to and including multiple doses of 20 mg/kg TID (60 mg/kg/day) for 4 days and alternatively a loading dose of 40 mg/kg followed by 20 mg/kg TID (60-80 mg/kg/day) for 2 days.

### **1.7.2 Pharmacokinetics**

[figure not shown]
After a single dose of GMI-1070 in healthy volunteers, mean values for  $C_{max}$ ,  $AUC_{(0-t)}$ , and  $AUC_{(inf)}$  increased in a dose-proportional manner, providing evidence of linear PK. The median values for  $T_{max}$  ranged from 0.341 to 0.417 hours and were not dependent on dose. There were no dose related trends in either CL or  $V_z$  and the mean elimination half-life ( $t_{1/2}$ ) ranged from 6.67 hours to 7.41 hours and was independent of dose. (Table 3)

**Table 3. GMI-1070 Pharmacokinetics Post Single Dose in Healthy Adults**

Parameter 	Cohort				
	2 mg/kg N=6	5 mg/kg N=6	10 mg/kg N=6	20 mg/kg N=6	40 mg/kg N=6
C max (µg/mL)	19.1±2.39	53.6±4.60	137±20.5	256±43.7	454±53.2
T max (h)	0.417	0.355	0.383	0.417	0.341
AUC (0-t) (hr*µg/mL)	117±19.5	288±37.9	794±104	1312±141	2563±423
AUC (inf) (hr*µg/mL)	120±17.7	291±38.9	802±109	1321±148	2582±431
kel (h  )	0.0941±0.0083	0.1028±0.0151	0.0976±0.0124	0.1058±0.0154	0.1007±0.0083
t 1/2 (h)	7.41±0.64	6.85±0.90	7.19±0.81	6.67±0.96	6.93±0.58
CL (mL/h/kg)	0.284±0.042	0.292±0.043	0.211±0.029	0.255±0.028	0.264±0.041
V z (L/kg)	0.181±0.022	0.171±0.017	0.130±0.006	0.145±0.011	0.157±0.022
Ue (mg)	140±13.3	332±28.0	709±71.5	1412±179	2755±524
Fe (% dose)	90.2±9.54	93.9±10.5	102±8.08	98.0±6.31	99.1±11.7
CL r (mL/min)	20.5±4.17	19.5±3.20	15.1±2.65	18.2±3.43	18.2±4.16

[figure not shown]
Arithmetic mean ± standard deviation (N) except for Tmax for which the median (N) is reported.

Analysis of the plasma concentration and urinary excretion data for GMI-1070 in healthy adults after IV administration of 5, 10, or 20 mg/kg every 8 hours for 4 days or 40 mg/kg x 1 + 20 mg/kg every 8 hours for 2 days indicates linear PK over that range of doses (Figure 2). The loading dose achieved steady state immediately. The elimination t1/2 was ~8 hours, a minimum of 89% of the dose was recovered in the urine, and CLr was less than filtration clearance, consistent with tubular reabsorption.

**Figure 2: Mean plasma concentrations of GMI-1070 after the final dose during intravenous administration of 5, 10, or 20 mg/kg every 8 hours or 40 mg/kg × 1 + 20 mg/kg every 8 hours to healthy adults under fasted conditions - semi-logarithmic axes**

Data from 14 subjects in the GMI-1070-103 study indicate that the pharmacokinetics of GMI-1070 in stable SCD subjects not in VOC are well characterized by a two-compartment model; estimates for clearance, volume of distribution,  $t_{1/2}$ , and  $CL_r$  were consistent with those in healthy volunteers. As seen in the mean plasma concentrations (Figure 3), there was excellent agreement between the observed plasma GMI-1070 concentrations and those predicted by the pharmacokinetic model for all patients. (Table 4)

**Figure 3: Observed (mean ± standard deviation) and model predicted plasma concentrations of GMI-1070 after intravenous infusion of 20 mg/kg (loading dose) and 10 mg/kg (maintenance dose) to patients with SCD — semi-logarithmic axes**

**Table 4. Pharmacokinetic parameters of GMI-1070-103**

Parameter	GMI-1070 20 mg/kg + 10 mg/kg  Arithmetic mean (SD) N = 14
Primary 	
Total plasma clearance (CL; mL/h/kg)	19.6 (6.42)
Volume of the central compartment (V1; mL/kg)	120 (30.7)
Intercompartmental clearance (CLD2; mL/h/kg)	31.6 (17.2)
Volume of the peripheral compartment (V2; mL/kg)	64.2 (19.6)
Secondary 	
Volume of distribution at steady state (V ss ; mL/kg)	184 (40.1)
Maximum observed drug concentration (C max ; µg/mL)	167 (48.4)
Area under the plasma concentration-time curve to infinity (AUC [inf] ; h x µg/mL)	1129 (367)
Apparent first-order distribution rate constant (α; h  )	0.8610 (0.3985)
Apparent first-order terminal elimination rate constant (β; h  )	0.0969 (0.0249)
Elimination half-life (t 1/2 ; h)	7.70 (2.38)
Tertiary 	
Renal clearance for the collection period (CL r ; mL/min)	18.0 (7.94)

SD = standard deviation.

1 The first dose was a loading dose and the second dose was administered 10 ± 1 hours later.

2 Primary parameters were those used to fit the model and secondary parameters were estimated from the primary parameters.

3 Tertiary parameters were estimated from the primary parameters plus the urinary excretion of GMI-1070.

### 1.7.3 Dose Selection

The initial dose used in this study, a 20 mg/kg loading dose followed by a 10 mg/kg dose every 12 hours for up to 7 days, was selected based on non-clinical pharmacokinetic/ pharmacodynamic (PK/PD) studies in a SCD mouse model as well as experience with human dosing in healthy volunteer studies, GMI-1070-101 and GMI-1070-102, and human dosing in stable SCD subjects not in VOC, study GMI-1070-103. The safety profile of GMI-1070 was excellent, including up to a 40 mg/kg loading dose followed by a 20 mg/kg dose every 8 hours, or a total of 60 mg/kg per day for 4.3 days. The PK profile from these clinical studies supports using a 20 mg/kg loading dose to achieve steady state immediately, and continuing dosing at 10 mg/kg every 12 hours to maintain plasma levels above a minimum concentration (Cmin) of 16-20 µg/mL associated with effect in the SCD mouse model.

As per study protocol section 8.2.5, the PK data from the first 10 subjects in this study were evaluated in an interim analysis to confirm the dose. The analysis was performed using a population PK model developed from rich datasets of the previous PK studies. In the population PK model there was no difference between healthy

subjects and those with SCD not in VOC. Because SCD subjects in VOC are in a different physiologic state and treatment paradigm than those not in VOC (most notably they may have higher cardiac output and are heavily hydrated), and clearance of GMI-1070 is through the kidney, it was not known if PK parameters would differ. This interim PK analysis was planned to confirm or adjust dose, if necessary, for the remainder of the study.

This interim PK analysis indicated that SCD subjects in VOC appear to have a higher rate of clearance of GMI-1070 as compared to the healthy volunteer and subjects with SCD not in VOC (as seen in studies GMI-1070-101, GMI-1070-102 and GMI-1070-103, respectively). None of the covariates examined (age, gender, weight, height, organ function or hemoglobin) appeared to explain this difference between the predicted and the observed levels. Half the subjects included in the interim PK analysis were between the ages of 14-25 years. The data, incorporated into the model, demonstrated a mean  $C_{min}$  of 11  $\mu\text{g/mL}$ , with the individual patient range between 4 – 24  $\mu\text{g/mL}$ . This is below the 16-20  $\mu\text{g/mL}$  minimum both desired based on non-clinical efficacy studies and expected based on previous human studies. The average time above 20  $\mu\text{g/mL}$  actually achieved is 7.2 hours (60.2%) of the dosing interval. In contrast, the expected time above  $C_{min}$  at the outset of the study was 90-100% of the dosing interval. Furthermore, the average time above 15  $\mu\text{g/mL}$ , which represents the lower end of the  $C_{min}$  target, is only 8.6 hours of a 12 hour dosing interval (71.9% of the dosing interval).

Non-clinical and biomarker data from the GMI-1070-103 study suggest that the levels of GMI-1070 achieved with the loading dose of 20 mg/kg followed by 10 mg/kg dose every 12 hours would likely still be within the range necessary to show a biological effect. Nevertheless, given the excellent safety profile seen to date and the desire to evaluate clinical effect at the original target plasma levels in the context of this Phase 2 study, the Sponsor has elected to adjust the dose to reach these original target levels. This is considered appropriate for all age groups in the study, as age was not identified as a covariate for PK behavior. As allowed in protocol section 8.2.5, the dose level is being adjusted to achieve the desired plasma concentration of GMI-1070.

PK modeling using the established population PK model and the new data suggests that a loading dose of 40 mg/kg followed by 20 mg/kg every 12 hours will result in a mean  $C_{min}$  of 21.4  $\mu\text{g/mL}$ . In addition, this will result in an average time above 20  $\mu\text{g/mL}$  of 10.3 hours of a 12 hour dosing interval (85.8% of the dosing interval).

Previous studies have evaluated doses up to and including this dose level (40 mg/kg followed by 20 mg/kg every 12 hours), and in fact up to a greater total daily dose (60-80 mg/kg/day in the GMI-1070-102 study) with minimal safety concerns. In addition, comparison of PK data across the 3 previous studies indicates that the slower clearance rate in earlier studies resulted in higher total exposure than that anticipated in SCD subjects in VOC (Table 5). Higher total exposure combined with minimal safety concerns seen in previous studies suggests that the increase in dose in SCD subjects with VOC is acceptable from a safety risk perspective.

**Table 5. Comparison of AUC and Cmax in the Phase 1 and Phase 2 Studies with GMI-1070 on Day 1 and at Steady State over a 24-hour Period**

Study Reference	Regimen, mg/kg (Load/Maintenance)	Day 1 Mean (SD)		Steady State Mean (SD)	
		C max	AUC (0-24)	C max	AUC (0-24)
102	20 TID (no load)	237 (54.9)	2268 (184)†	349 (35.6)	4323 (381)†
102	40/20	445 (55.8)	2896 (203)†	292 (21.7)	3768 (282)†
103	20/10	167 (48.4)	1402*	116*	1108*
201	20/10	190 (55.2)*	1058 (449)*	105 (34.3)*	767 (347)*
New Dose 201	40/20	380 (110.4)*	2116 (897)*	210 (68.8)*	1534 (694)*

† AUC(0-24) calculated from AUC(0-8) data

\* Modeled PK data

Given the excellent safety profile seen to date and that Cmin is the PK parameter selected to set the dose, the dose will be adjusted to a loading dose of 40 mg/kg followed by 20 mg/kg every 12 ± 2 hours in order to achieve the desired plasma concentrations.

## 2 STUDY OBJECTIVES AND PURPOSE

### 2.1 Rationale for this Study

GMI-1070 is a potent, rationally designed glycomimetic inhibitor of E-, P-, and L-selectins *in vitro*. GMI-1070 has been shown to inhibit inflammation in several animal models of disease, including the VOC of SCD. This study drug is being developed for the treatment of VOC in SCD. In the present study, subjects 12 to 60 years of age who are hospitalized for VOC will be evaluated for the efficacy, safety, and PK of GMI-1070.

Amendment 1 expanded assessment of GMI-1070 from adults aged 16 to 45 to adolescents aged 12 to 15 years. As an inherited disease, sickle cell presents early in childhood and patients in all age groups, from infancy through adulthood, experience VOC. Adolescents generally have fewer co-morbidities and lower incidence of chronic pain and opioid narcotic use, such that GMI-1070 may have a greater treatment effect in younger patients experiencing VOC than adults. GMI-1070 has been well-tolerated in clinical trials to date; and based on the mechanism of action no differences in safety or efficacy would be expected in children as compared to adults. Thus, inclusion of adolescent subjects in clinical studies throughout clinical development is a critical component of the program.

Safety and PK data collected in the 2 prior studies of IV GMI-1070 in healthy adults and 1 study in subjects with stable SCD, have demonstrated an excellent safety profile and linear, predictable PK parameters at a range of doses for up to 4 days of treatment. In addition to the human safety data and based on results of GMI's nonclinical testing in juvenile monkeys and rats, GMI believes that assessment in adolescents aged 12 to 15 years would be safe and well-tolerated.

Amendment 2 revised eligibility criteria in response to further review of criteria in similar studies, with the consensus of the study investigators and DSMB Chair. These criteria included changing the upper age limit to 60, limits on previous transfusions and frequency of recent hospitalizations for VOC.

Amendment 3 modified the dose of GMI-1070 to a loading dose of 40 mg/kg followed by 20 mg/kg every  $12 \pm 2$  hours. This was in response to the PK interim analysis of the first 10 subjects as per protocol section 8.2.5. The PK interim analysis indicated that SCD subjects in VOC appear to have a higher rate of clearance of GMI-1070 as compared to healthy volunteers and subjects with SCD not in VOC (as seen in studies GMI-1070-101, GMI-1070-102, and GMI-1070-103 respectively). The dose level was correspondingly increased to achieve the desired plasma concentration of GMI-1070.

Amendment 4 revised eligibility criteria in response to further review of criteria in similar studies, with the consensus of the study investigators and DSMB Chair. These criteria revisions included allowing subjects to be enrolled within 24 hours of presentation to the ED or after up to 2 days of outpatient parenteral treatment, and changing the limits on previous transfusions.

The present study seeks to build on these data by evaluating the safety and PK of two dose levels of GMI-1070 in subjects 12 to 60 years of age experiencing VOC. This study will also evaluate efficacy of GMI-1070 at two dose levels and gather data on biomarkers of adhesion and inflammation, and additional clinical activity with respect to pain and complications. Moreover, the dose adjustment will allow for the comparison of two dose levels in the same study, adding to the clinical pharmacology dataset for GMI-1070 in the treatment of VOC.

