#### **5.1.4 Allocation of Subjects to Treatment**

Subjects will be randomized in a 1:1 ratio to receive either GMI-1070 or placebo. Randomization blocks will be stratified by site using an IVRS. Instructions on use of the IVRS will be included in the Study Reference Manual.

Once IRB/IEC approval for Amendment 3 (Protocol Version 4.0) is received, all new subjects should be enrolled at the new dose level of GMI-1070 or placebo.

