## **8 STATISTICAL ANALYSIS**

The statistical analyses described in this section will be performed as further outlined in the Statistical Analysis Plan (SAP), which will be finalized prior to completion of the clinical portion of the study and will be included in the Clinical Study Report for this protocol. The SAP will give a detailed description of the summaries and analyses (primary and secondary) that will be performed. Changes from analyses planned in the protocol will be documented in the SAP. If changes to principal features stated in the protocol are required, these will be documented in a protocol amendment.

For the purpose of analysis, the end of study is defined as the date of final database lock.

All variables will be summarized at specified time points by dose level. Categorical variables will be summarized using counts (n) and percents (%) and will be presented in the form n (%). Continuous variables (eg, height, weight) will be summarized using the number of observations, mean, standard deviation and/or standard error, and minimum and maximum values.

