**8.2.7 Study Drug Interim Analysis**

An interim safety review will be performed by the DSMB and Sponsor Medical Monitor after treatment of the first 10 subjects under 18 years of age, and additionally after 25 and 50 subjects of all ages have been treated with the study drug. This review will include AEs and any other pertinent information. The DSMB and the Sponsor's Medical Monitor will review select data listings to ascertain the existence of any safety concerns for which the study should be terminated, as described in Section 6.3.6.4. The Sponsor's Medical Monitor will remain blinded.

In addition to the safety review, the DSMB and a sponsor representative (not otherwise involved in the study execution) will also review the efficacy (clinical activity) results in the first 50 subjects. Stopping criteria for the efficacy interim analysis are discussed in Section 8.3.2.

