### **8.3.2 Sample Size**

Evaluable subjects are those who have received at least 1 dose of study medication. Subjects in the evaluable population will be used to determine when an adequate sample size has been achieved.

The study will enroll until a total of approximately 76 evaluable subjects (defined as those who have received at least 1 dose of study medication) have been enrolled. An interim analysis will be done after the first 50 subjects have completed the follow-up day 7 post last dose, to assess safety and efficacy. The efficacy test statistic for this interim analysis will be compared to a critical value corresponding to a 2-sided alpha of 0.005. To control study wise Type I error, an alpha spending approach will be utilized. The final analysis will then compare the test statistic to a critical value corresponding to 2-sided alpha of 0.045. Futility criteria will also be considered; these will be specified in detail in the statistical analysis plan.

A previous pilot study of treatments for pain in SCD showed the mean pain duration in placebo group is 103 hours with a standard deviation of 60 hours. The original protocol sample sizing was done as follows. Assuming that the variances are the same in both groups and anticipating that the study drug will decrease pain duration by 40%, a total of at least 76 subjects (38 subjects each group) will be needed to detect a 40% decrease in VOC resolution and to achieve 83% power with a 2-sided alpha of 0.045.

With the addition of a second dose level, the power calculation for the study has been updated to compare the treatment difference between the placebo group and the pooled active group (ie, both dose levels combined). The sample sizing assumes that the placebo group has a mean pain duration of 103 hours with a standard deviation of 60 hours, and that both groups – placebo and pooled active groups – share a common standard deviation. Anticipating that the placebo and pooled active groups will each have about 38 subjects (ie, the pooled group will have 19 subjects from each of the dose levels) the study will have an 89% power to detect a 43.8% decrease in VOC duration with a 2-sided alpha of 0.045.

The sample size is also expected to provide initial safety and PK conclusions sufficient to contribute to the design of subsequent trials.

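### Dose level follows enrolment period, not randomization, yet the protocol promises dose-level conclusions without a stage term or same-stage placebo contrasts

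*Protocol*

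**What the plan says.** - **Objective and claim.** The primary objective (Protocol 2.2.1) is the effect on time to resolution at two dose levels. Section 2.1 adds that "the dose adjustment will allow for the comparison of two dose levels in the same study".
- **Allocation.** Section 5.1.4: "Subjects will be randomized in a 1:1 ratio to receive either GMI-1070 or placebo", in blocks stratified by site only. Once a site has approval for Amendment 3 (Version 4.0), "all new subjects should be enrolled at the new dose level of GMI-1070 or placebo".
- **Eligibility.** Section 2.1 records changes before the dose switch (Amendment 2: upper age limit, transfusion and hospitalization limits) and after it (Amendment 4). Of the latter it says: "These criteria revisions included allowing subjects to be enrolled within 24 hours of presentation to the ED". Amendment 4 also admits subjects after up to two days of outpatient parenteral treatment and alters the transfusion limits again.
- **Models.** The primary ANCOVA (8.2.3.1) adjusts for sex, age and Hemoglobin A. Site and age enter if sample size permits (8.2.3). The secondary models (8.2.3.2) use sex and age, and some add time and a baseline value. A fixed-sequence test procedure is named without its steps.
- **Dose-level output.** Section 8: "All variables will be summarized at specified time points by dose level".
- **Sample size.** Section 8.3.2: "The study will enroll until a total of approximately 76 evaluable subjects". Power is for placebo against both doses pooled, on the expectation that "the pooled group will have 19 subjects from each of the dose levels".
- **Interim.** In Section 8.2.7 the DSMB and a sponsor representative "will also review the efficacy (clinical activity) results in the first 50 subjects". The criterion in 8.3.2 is a two-sided 0.005. Nothing is said about the dose mix.

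**The concern.** No subject is ever randomized between the two doses. Which dose an active subject receives depends on when the site took up Version 4.0, so dose and stage coincide completely among active subjects. Anything else that moves between stages, such as case mix after the eligibility changes, participating sites or local practice, is carried into a dose-level contrast. The endpoint clock starts at the first dose (8.2.3.1). A later entry window, or entry after outpatient treatment, could therefore plausibly change the measured time.

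At stake is the dose-level reading of the primary objective. Old against new dose is a before-and-after comparison, but Section 2.1 presents it as something the study will deliver. One dose against the whole placebo group would borrow half its controls from the other stage. The 50-subject look has a related problem: a pooled result may reflect mainly one dose, and nothing in the protocol asks for the two stages to be shown separately.

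**Working it through.** **Inputs (Protocol 8.3.2).** Placebo mean 103 h, common SD 60 h, 38 per arm, 19 anticipated per dose, two-sided alpha 0.045 at the end and 0.005 at 50 subjects. Effects: 40% (0.40 × 103 = 41.2 h) in the original sizing, 43.8% (0.438 × 103 = 45.1 h) in the updated one.

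**1. The plan's own power.** Noncentral t, 38 against 38, 74 df: 82.8% for 41.2 h and 89.0% for 45.1 h. The stated 83% and 89% reproduce.

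**2. Bias from a stage shift.** Let mean time differ by D hours between stages for reasons other than dose, with 19 active and 19 placebo in each stage.
- Pooled active against pooled placebo: both arms carry D/2, so bias = 0.
- New against old dose: bias = D.
- One dose against all 38 placebo: half the placebo subjects come from the other stage, so bias = D/2, with opposite signs for the two doses.
- One dose against same-stage placebo: bias = 0.

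The documents give no value for D. For an assumed 10 to 30 h, D/2 is 5 to 15 h. Against the updated target: 5/45.1 = 11% and 15/45.1 = 33%.

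**3. False-positive rates.** Simulation with 20,000 runs, no drug effect, nominal 0.045:

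| Assumed D (h) | New vs old dose | New dose vs all placebo | New dose vs same-stage placebo | Pooled active vs placebo |
|---|---|---|---|---|
| 12 | 8% | 6% | 4.5% | 4.6% |
| 20 | 16% | 8% | 4.5% | 4.1% |
| 30 | 30% | 12% | 4.5% | 4.0% |

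**4. Price of same-stage placebo.**
- SE, 19 against 38: 60 × √(1/19 + 1/38) = 16.9 h.
- SE, 19 against 19: 60 × √(2/19) = 19.5 h. Ratio 1.155.
- Power at 0.045, 19 against 38: 65% (40% effect) and 73% (43.8% effect), valid only if D = 0.
- Power at 0.045, 19 against 19: 52% and 60%.
- Dose against dose, 19 against 19: the difference detectable with 80% power is 57 h, which is 55% of the placebo mean.

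**5. Dose mix at the 50-subject look.** With 1:1 allocation there are about 25 active subjects. If the switch came after S subjects (S up to 50), about S/2 of them had the old dose. The anticipated 19/19 split implies S = 38, giving 19 of 25 (76%) on the old dose and 6 on the new. Other values of S give:

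| S | 10 | 20 | 25 | 30 | 38 | 50 |
|---|---|---|---|---|---|---|
| Old-dose share at the look | 20% | 40% | 50% | 60% | 76% | 100% |

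Illustration on the 76/24 mix, with assumed effects:
- Old dose 0%, new dose 40%: the pooled effect at the look is 0.24 × 40% = 9.6% (power 1.3% at 0.005) and 20% at the end (power 30% at 0.045).
- Old dose 20%, new dose 40%: 24.8% at the look (power 8.7%) and 30% at the end (power 58%).

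**The case against.** The strongest reply is that the contrast on which the trial is powered is unaffected. Placebo was randomized 1:1 in both stages, so a stage shift falls on both arms. This stands. A reader might infer that the primary result is confounded; the documents do not support that. The pooled contrast is a fair comparison of a two-dose mixture with placebo.

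Second, the protocol specifies no test of one dose against all placebo, and the SAP, which was not available here, may define dose-level contrasts and the fixed sequence. This stands in part. The D/2 bias is conditional on that contrast being used. It is also too strong to say that no analysis separates the stages, since Section 8 plans summaries by dose level. But the protocol itself lists its model covariates, rewrote its sample size for the new dose, and still makes the two-dose claim without qualification.

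Third, the Section 2.1 sentence goes on to speak of the clinical pharmacology dataset, so it may not promise an efficacy comparison. However, the sentence just before it speaks of evaluating efficacy at two dose levels, and Section 2.2.1 makes two dose levels the primary objective.

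Fourth, the eligibility changes do not coincide with the switch: Amendment 2 came before it and Amendment 4 after. Nor can all of them be called a widening, since the direction of the transfusion changes is not given in Section 2.1. This is correct, but the confounding argument needs only that the stages may differ. Same-stage placebo also handles Amendment 4, because treatment was randomized throughout the later stage.

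**Conclusion.** The point holds for dose-level conclusions and not for the powered pooled contrast. Dose against dose is open to bias by the full stage shift D. One dose against all placebo, if it is used, is open to bias by about D/2: 5 to 15 h, or 11% to 33% of 45.1 h, for D between 10 and 30 h. That range of D is an assumption, as are the even 19/19 split and the common SD of 60 h.

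A reader might also infer that the 50-subject look mostly judges the earlier dose. That follows from the anticipated split (about 19 of 25 active subjects), but the enrolment count at the switch is not stated, and the old dose is in the majority only if the switch came after more than 25 subjects. Nor does the protocol treat the earlier dose as inactive: Section 1.7.3 reports a mean minimum concentration of 11 µg/mL against a 16–20 µg/mL target, but expects those levels still to be within a range with biological effect.

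**What to change.** 1. Add stage (protocol version at randomization: before 4.0, or 4.0 and later) as a factor in the primary and other efficacy models.
2. Estimate each dose against placebo subjects randomized in the same stage. A three-level treatment factor (placebo, old dose, new dose) together with the stage factor does this directly.
3. In Section 2.1, describe old against new dose as a non-randomized, exploratory comparison.
4. Report the 50-subject look by stage as well as pooled.

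**Cost.** Amendment and SAP wording; one degree of freedom for stage and a second when the doses are separated; about 15% wider standard errors for dose-level estimates than with all placebo; and power of only about 52% to 60% for each dose against 19 same-stage placebo subjects. Dose-level results should be presented with that limit in view.

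Confining the futility rule to new-dose-stage subjects is not recommended. On the 19/19 split it would rest on about 6 against 6, with a standard error of 60 × √(2/6) = 34.6 h against a 45.1 h effect, and the protocol leaves futility detail to the SAP.
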